From AE data reported following LOXO-305 administration in healthy volunteers in the LOXO-BTK-20014 study, all TEAEs (headache, nausea, and vomiting) were Grade 1 in severity and considered related to LOXO-305. All 3 events were reported by 1 subject and resolved within 1 to 1.5 days (data on file at the time of protocol development). From preliminary AE data reported following LOXO-305 administration in healthy volunteers in the LOXO-BTK-20006 study, all TEAEs (intermittent belching, bloating, insect bite, aphthous ulcer, nausea, intermittent diarrhea [x2], muscle twitch) were Grade 1 in severity and bloating, intermittent diarrhea, and intermittent belching were considered related to LOXO-305. All 7 AEs were reported by 3 subjects and all events resolved prior to End of Treatment (EOT; data on file at the time of protocol development). From preliminary AE data reported following LOXO-305 administration in healthy volunteers in Cohort 1 of the LOXO-BTK-20017 study, there was 1 TEAE (headache), observed in the 300 mg LOXO-305 Cohort which was Grade 1 in severity and considered related to LOXO-305. The event resolved within 2 hours (data on file at the time of protocol development).

[figure not shown]
To date, there have been no clinically significant abnormal findings in vital signs and ECG data in the studies investigating LOXO-305 conducted in healthy volunteers.

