#### 8.6. Safety and Tolerability Assessments

#### 8.6.1. Adverse Events

All AEs will be coded using the Medical Dictionary for Regulatory Activities (MedDRA) Version 23.1. All AEs will be assigned severity grade using National Cancer Institute Common Terminology Criteria for Adverse Events (CTCAE) Version 5.0.

A treatment-emergent adverse event (TEAE) will be defined as an AE that starts during or after the first dose repaglinide, or starts prior to the first dose and increases in severity after the first dose.

A treatment-related TEAE will be defined as a TEAE with a relationship of related to the study treatment, as determined by the investigator.

If deemed related to study treatment, the assignment of TEAEs to treatments will be as follows:

- A TEAE occurring during or after Day 1 dosing and prior to Day 2 dosing will be assigned to 0.5 mg repaglinide
- A TEAE occurring during or after Day 2 dosing and prior to Day 12 dosing will be assigned to 200 mg LOXO-305
- A TEAE occurring during or after Day 12 dosing will be assigned to 200 mg LOXO-305 + 0.5 mg repaglinide

All AEs will be listed. In addition to the data recorded in the database, the listings will include derived onset time and duration. Onset time will be calculated from the time of the last dose for TEAEs only.

The frequency of subjects with TEAEs and the number of TEAEs will be summarized for the following categories:

• TEAEs (overall, serious, leading to discontinuation, and leading to death) by treatment

- TEAEs by severity and treatment
- Treatment-related TEAEs (overall, serious, leading to discontinuation, and leading to death) by treatment
- Treatment-related TEAEs by severity and treatment

The frequency of subjects with TEAEs will be summarized separately for all TEAEs and treatment-related TEAEs by the following:

- System organ class, preferred term, and treatment
- Preferred term and treatment

For the AE data the following rules will apply:

- For the derivation of TEAE status: If the start date/time of an AE is incomplete or missing, an AE will be assumed to be a TEAE, unless the incomplete start date/time or the end date/time indicates an AE started prior to the first dose.
- For the derivation of treatment-related TEAE status: If the study treatment relationship for a TEAE is missing, a TEAE will be assumed to be a treatment-related TEAE.

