- For the derivation of onset time: If the start date/time of an AE is missing, onset time will not be calculated. If the start date/time of an AE is incomplete, where possible, the minimum possible onset time will be calculated and presented in '≥DD:HH:MM' format (eg, if the date/time of the last dose is 01MAY2019/08:00 and recorded start date/time of an AE is 03MAY2019, then the minimum possible onset time will be calculated by assuming the AE started at the first hour and minute of 03MAY2019 [03MAY2019/00:00], thus will be presented as onset time ≥01:16:00 in the listing).
- For the derivation of duration: If the end date/time of an AE is missing, duration will not be calculated. If the start or end date/time of an AE is incomplete, where possible, the maximum possible duration will be calculated and presented in '≤DD:HH:MM' format (eg, if the start of an AE date/time is 01MAY2019/08:00 and its recorded end date/time is 03MAY2019, then the maximum possible duration will be calculated by assuming the AE ended at the last hour and minute of 03MAY2019 [03MAY2019/23:59], thus will be presented as duration ≤02:15:59 in the listing).
- For the calculation of summary statistics: If the severity of a TEAE is missing, a TEAE will be counted under the maximum severity possible, up to Grade 4 in the absence of a fatal outcome.
- For the calculation of summary statistics: If a subject experienced multiple TEAEs with the same preferred term for the same treatment, this will be counted as 1 TEAE for that treatment under the maximum severity recorded.

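### SAP 8.6.1 promises a number of TEAEs, but its rule for repeat events turns that number into a count of subject-by-preferred-term-by-treatment combinations

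*SAP*

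**What the plan says.** SAP 8.6.1 (Adverse Events) announces its main AE tables with "The frequency of subjects with TEAEs and the number of TEAEs will be summarized for the following categories". The categories are overall, serious, leading to discontinuation, leading to death, and by severity, for all TEAEs and again for treatment-related TEAEs. The tables by system organ class and preferred term, and by preferred term alone, promise subject frequency only.

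The rules for AE data at the end of the same section include one that applies to the calculation of summary statistics in general: "If a subject experienced multiple TEAEs with the same preferred term for the same treatment, this will be counted as 1 TEAE for that treatment", at the highest severity recorded.

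The treatment windows are also set in 8.6.1:

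- Repaglinide alone: "A TEAE occurring during or after Day 1 dosing and prior to Day 2 dosing will be assigned to 0.5 mg repaglinide".
- LOXO-305 alone: "A TEAE occurring during or after Day 2 dosing and prior to Day 12 dosing will be assigned to 200 mg LOXO-305".
- Combination: "A TEAE occurring during or after Day 12 dosing will be assigned to 200 mg LOXO-305 + 0.5 mg repaglinide".

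The section also says that all AEs will be listed. Protocol 8.4 promises AE incidence by severity and relationship and gives no rule for counting events.

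**The concern.** A subject count and an event count answer different questions. The first says how many people were affected; the second adds how often. Collapsing repeats of a preferred term is right for the first. Applied to the second, it removes the only information that the event count adds.

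Two serious events of the same term in one subject under one treatment would appear as one. A Grade 1 and a Grade 2 episode would appear as a single Grade 2 event. The secondary objective is the safety and tolerability of multiple doses of LOXO-305, alone and with repaglinide, so recurrence under repeated dosing is relevant to it. The treatment columns also cover windows of unequal length, so the loss need not be the same in each.

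**Working it through.** **Reading the two provisions together.** The plan states no figure to reproduce, so the first check is textual. The tables promise a number of TEAEs. The rule is introduced for the calculation of summary statistics without restriction, and its unit is a TEAE, not a subject. Nothing else in the SAP or protocol limits it or defines a separate event count. The maximum-severity clause has no function in the system organ class and preferred-term tables, which are not split by severity. It operates in the severity tables, and those promise an event count.

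**Worked example (hypothetical).** Between Day 2 and Day 12 dosing, one subject has five headaches (four Grade 1, one Grade 2) and one nausea. Events: 5 + 1 = 6. Under the rule: 1 + 1 = 2, and the four Grade 1 headaches leave the severity table.

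**Window lengths.**

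- Repaglinide alone: Day 1 to Day 2 = 1 day.
- LOXO-305 alone: Day 2 to Day 12 = 10 days.
- Combination: Day 12 to EOT on Day 16 = 4 days for all AEs. Related AEs continue to the follow-up call 7 ± 2 days later, so 4 + 5 = 9 to 4 + 9 = 13 days.

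The SAP states these windows only for related TEAEs. I apply them to all TEAEs as an assumption.

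**Size.** Recurrence rates are not in the documents. Assume that episodes of one preferred term in one subject follow a Poisson distribution with mean m over the window. Expected events per subject are m and the expected collapsed count is 1 − exp(−m), so

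share lost = 1 − (1 − exp(−m))/m.

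*Anchor from the documents.* Protocol 1.4.1 gives fatigue as the most frequent TEAE in the patient study, at 12.8%. Setting 1 − exp(−m) = 0.128 gives m = −ln(0.872) = 0.137, and the share lost is 1 − 0.128/0.137 ≈ 6.5%. In 16 subjects that is 16 × 0.137 = 2.19 events against 16 × 0.128 = 2.05 counted, a difference of about 0.14 of an event. The 12.8% comes from patients on 25 to 300 mg QD, not from a 10-day window in healthy subjects, so it sets a scale and is not a forecast.

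*Higher assumed means.*

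| m | Incidence implied | Share lost |
|---|---|---|
| 0.5 | 39% | 21% |
| 1 | 63% | 37% |
| 2 | 86% | 57% |

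*By window, at an equal assumed daily rate (m = rate × days).*

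| Rate per subject-day | 1 day | 4 days | 10 days |
|---|---|---|---|
| 0.01 | 0.5% | 2.0% | 4.8% |
| 0.05 | 2.5% | 9.4% | 21.3% |
| 0.1 | 4.8% | 17.6% | 36.8% |

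The loss is never exactly zero for the one-day window, and it rises with window length.

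**The case against.** The best defence is that this is a disclosed convention: the SAP says how a TEAE is counted, the protocol promises only incidence, and collapsing to maximum severity serves incidence. The rule may also have been meant for subject counts only, and the TFL shells, which SAP 1 says describe the tables in detail, were not available for this review and may show that. Part of this stands: intent cannot be settled from the two documents. The wording still counts TEAEs where the same section promises their number. Nor does the rule work well as a pure subject rule, because it takes the maximum within a preferred term and does not place a subject whose grades differ across terms.

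The mitigation also stands. All AEs are listed with onset and duration, up to 16 subjects are planned, SAEs are notified within 24 hours (Protocol Appendix 1), and SAP 8.6.6 plans no inference on safety data. Repeat events are not concealed.

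A reader might infer more than the documents support:

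- *That only the longer windows lose events.* Two headaches within the one-day repaglinide window collapse as well. The 10-day window is not the only long one either, since related AEs in the combination window run 9 to 13 days.
- *That a fifth to a half of events will be lost.* Losses of 21% to 57% require 39% to 86% of subjects to have the same term, and no incidence in the documents approaches that.
- *That the table is bound to disagree with the listing.* It does so only if a term recurs in one subject within one treatment.
- *That the sponsor's own data show the problem.* Protocol 1.4.1 marks diarrhea as occurring twice in LOXO-BTK-20006, but does not say whether in one subject or under one treatment. The terms listed make eight events if that mark means two, yet the text gives seven AEs.

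**Conclusion.** The point holds as a conflict within SAP 8.6.1. Applied as written, the number of TEAEs, including the serious and by-severity counts, is the number of subject-by-preferred-term-by-treatment combinations. It departs from the listing when a term recurs in a subject within a treatment, and at equal daily rates the departure is larger in longer windows.

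The documents do not fix its size. Zero without recurrence and about 6.5% at a 12.8% incidence are the values closest to what they report; 21% or more depends on assumed means of at least 0.5 episodes per subject. All non-zero figures rest on the Poisson assumption. The consequence is minor and descriptive, and the PK comparison is unaffected. It is worth correcting before database lock because the correction is specific and nearly free.

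**What to change.** Replace the rule in SAP 8.6.1 with two statements:

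- In subject counts, a subject with several TEAEs of one preferred term under one treatment contributes once, at the highest severity recorded.
- In the number of TEAEs, each TEAE contributes separately, at its own severity.

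Align the TFL shells with this. The cost is a sentence or two in the SAP and a check of the shells; no new data are needed. The only downside is that event counts may be slightly larger.

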#### 8.6.3. Vital Signs Parameters

All vital signs parameters with changes from baseline will be listed; any value outside the clinical reference range will be flagged, and whether the out of range value was deemed clinically significant or not clinically significant will be indicated.

The observed results and change from baseline for all vital signs parameters will be summarized descriptively by treatment and timepoint.

#### 8.6.4. 12-lead Electrocardiogram Parameters

All 12-lead ECG parameters with changes from baseline will be listed; any value outside the clinical reference range will be flagged, and whether the out of range value was deemed clinically significant or not clinically significant will be indicated.

The observed results and change from baseline for all 12-lead ECG parameters will be summarized descriptively by treatment and timepoint. QTcF values that are > 450 msec and increase from baseline > 30 msec will be flagged in the data listing.

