#### 4.4. Exclusion Criteria

The following will exclude potential subjects from the study:

- 1. History or presence of any of the following, deemed clinically significant by the Investigator (or designee), and/or Sponsor:
  - a. liver disease
  - b. pancreatitis
  - c. peptic ulcer disease
  - d. intestinal malabsorption
  - e. cholecystectomy
  - f. gastric reduction surgery
  - g. history or presence of clinically significant cardiovascular disease:
    - i. Myocardial infarction or cerebrovascular thromboembolism within 6 months prior to Day 1
    - ii. Symptomatic angina pectoris within 6 months prior to Day 1
    - iii. New York Heart Association Class ≥ 2 congestive heart failure within 6 months prior to Day 1
    - iv. Congenital prolonged QT syndrome
    - v. Ventricular pre-excitation syndrome (Wolff-Parkinson White syndrome)
    - vi. Arrhythmia (excluding benign sinus arrhythmia) or history of arrhythmia requiring medical intervention
    - vii. Ventricular dysfunction or risk factors for Torsades de Pointes (eg, heart failure, cardiomyopathy, family history of Long QT Syndrome)
    - viii. Significant screening ECG abnormalities:
      - 1. left bundle-branch block
      - 2. second-degree atrioventricular (AV) block, type 2, or third-degree AV block
      - 3. QT interval corrected for heart rate using Fridericia's method (QTcF) is > 450 msec
      - 4. ECG findings deemed abnormal with clinical significance by the Investigator (or designee) at Screening, Check-in (Day -1), or prior to dosing on Day 1.

CONFIDENTIAL

Protocol Covance Study: 8425120 Protocol Reference: LOXO-BTK-20016

> Rechecks of out-of-range values for these ECG parameters that are not clinically significant (as determined by the Investigator [or designee]) will be permitted up to 2 times during Screening, Check-in (Day -1), and predose on Day 1 to confirm eligibility for the study if the values fall within the ranges stated above.

- 2. Subjects with out-of-range, at-rest (ie, supine for at least 5 minutes) vital sign measurements at Screening, Check-in (Day -1), or prior to dosing on Day 1, including:
  - a. oral body temperature > 37.5°C
  - b. pulse rate < 50 or > 99 beats per minute
  - c. systolic BP < 89 or > 139 mmHg
  - d. diastolic BP < 50 or > 89 mmHg
  - e. oxygen saturation < 95% (room air).

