#### **7.2.1.** Adverse Events

AE definitions; assignment of severity, causality, action taken, and outcome; and procedures for reporting SAEs are detailed in Appendix 1.

Subjects will be asked a non-leading HDYF? Question such as "Have there been any changes in your health status since Screening/since you were last asked?" at the timepoints specified in Appendix 4 (ie, at Screening [after the ICF is signed], at Check-in [Day -1], at each postdose vital sign measurement, and at an appropriate time for all other days). Subjects will also be encouraged to voluntarily report AEs occurring at any other time through the EOS.

Covance Study: 8425120 Protocol Reference: LOXO-BTK-20016

AEs, whether volunteered, identified by the subject's responses to HDYF? Inquiries, or noted on physical examination, ECG, vital sign measurements, or clinical laboratory evaluations, will be recorded throughout the study (ie, from signing of the ICF until EOS [or ET if the subject discontinues from the study and does not complete a follow-up phone call]), either as subject medical history (if the event is reported as beginning prior to signing of the ICF or if the event occurs prior to study drug administration on Day 1 and is assessed as not related to study procedures by the Investigator [or designee]) or as AEs (if the event occurs after signing of the ICF but prior to study drug administration on Day 1 and is assessed as related to study procedures by the Investigator [or designee], or if the event occurs after study drug administration on Day 1 through EOT or ET regardless of relationship to study drug). From EOT or ET through EOS, only AEs assessed as related to study drug by the Investigator (or designee) are to be reported. All SAEs that develop from the time of ICF signing until EOS (or ET, if the subject discontinues from the study and does not complete a follow-up phone call) are to be reported.

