## 8.4. Safety Analysis

All safety assessments, including AEs and SAEs, vital sign measurements, clinical laboratory results, physical examination results, concomitant medications, and 12-lead ECGs, will be tabulated and summarized where possible, using descriptive methodology, as needed, by treatment and timepoint. Unless otherwise specified, baseline value is defined as the last non-missing measurement before administration of study drug on Day 1. No formal statistical analyses are planned for the safety data. All safety data will be listed by subject.

Concomitant medications will be coded using the World Health Organization (WHO) Drug Dictionary (WHO Drug Global B3, September 2019) and AEs will be coded using MedDRA Version 22.1 (or higher). The incidence of AEs will be presented by severity and by relationship to study drug as determined by the Investigator ([or designee], Appendix 1 for AE reporting). All TEAEs will be summarized by system organ class (SOC) and preferred term (PT).

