- u. The EOT is defined as when the subject is released from the CRU following completion of all assessments through Day 16 (EOT) or ET. The ET is defined as when the subject is released from the CRU if the subject terminates the study early. Vital sign measurements, ECG, and abbreviated physical examination results are to be available for review by the Investigator (or designee) prior to subject release from the CRU at the EOT visit. Clinical laboratory evaluation results for clinical chemistry, hematology, coagulation, and UA and serum pregnancy test results (female subjects only) are to be available for review by the Investigator (or designee) prior to subject release from the CRU at the EOT visit and prior to subject release from the CRU at the ET visit, if available.
- v. Clinical laboratory evaluations and serum pregnancy test (female subjects only) will be performed on the day prior to subject release from the CRU (Day 15) if the subject completes the study (EOT). Clinical laboratory evaluations and serum pregnancy test (female subjects only) will be performed on the day of subject release from the CRU if the subject terminates early (ET).
- w. To be conducted 7 days (± 2 days) following EOT (Day 16) or ET. The EOS is defined as when the subject is contacted by the CRU for a follow-up phone call 7 days (± 2 days) after the EOT visit or ET visit to determine if any SAE or study drug-related AE has occurred since the EOT or ET visit. All subjects who received LOXO-305 (including subjects who are terminated early) will receive a follow-up phone call.

z. Denotes predose sample collection only.

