#### 1. INTRODUCTION

This SAP has been developed after review of the clinical study protocol (Final Version 1.0 dated 05 October 2020) and electronic case report form.

This SAP describes the planned analysis of the pharmacokinetic (PK) and safety and tolerability data from this study. A detailed description of the planned TFLs to be presented in the clinical study report (CSR) is provided in the accompanying TFL shells document.

In general, the analyses are based on information from the protocol, unless they have been modified by agreement with Loxo Oncology, Inc. A limited amount of information about this study (eg, objectives, study design) is given to help the reader's interpretation. This SAP must be finalized prior to the lock of the clinical database for this study. When the SAP and TFL shells are approved, they will serve as the template for this study's CSR.

This SAP supersedes any statistical considerations identified in the protocol; where considerations are substantially different, they will be so identified. If additional analyses are required to supplement the planned analyses described in this SAP, they may be performed and will be identified accordingly in the CSR. Any substantial deviations from this SAP will be agreed with Loxo Oncology, Inc. and identified in the CSR.

This SAP is written with consideration of the recommendations outlined in the International Conference on Harmonisation (ICH) E9 guideline *Statistical Principles for Clinical Trials* and ICH E3 guideline *Structure and Content of Clinical Study Reports*. 

The document history is presented in Appendix 1.

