#### 8.1.2. Repeat and Unscheduled Readings

For vital sign measurements and 12-lead ECG data only, any predose value recorded in addition to the original value or a postdose value recorded within 15 minutes of the original value will be defined as a repeat value; any postdose value recorded more than 15 minutes after the original value will be defined as an unscheduled value. For all other data types (eg, laboratory values), any value recorded in addition to the original value will be defined as an unscheduled value.

The original scheduled value will be used in all calculations post dose. In the event of any repeats or unscheduled measurements taken pre-dose the values will be considered when determining the baseline value.

Post dose repeats, unscheduled assessments, and ET measurements will be excluded from all calculations, with the exception of the baseline derivation (see Section 8.1.3).

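### Does it matter that SAP 8.6.4 leaves open whether its two QTcF listing criteria apply jointly or separately?

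*SAP*

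**What the plan says.** SAP 8.6.4 has two flagging provisions for ECG listings. The general one covers every ECG parameter: changes from baseline are listed, "any value outside the clinical reference range will be flagged", and each out-of-range value carries a clinical-significance call. The QTcF one reads "QTcF values that are > 450 msec and increase from baseline > 30 msec will be flagged in the data listing". The section also has observed values and changes from baseline summarised by treatment and timepoint.

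SAP section 1 says that the detailed description of the tables, figures and listings "is provided in the accompanying TFL shells document". Those shells are approved together with the SAP and are not among the documents reviewed here.

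The protocol sets no QTcF flag rule. Its safety analysis (section 8.4) is descriptive and states that "All safety data will be listed by subject". Among the screening ECG abnormalities in section 4.4 it lists "QT interval corrected for heart rate using Fridericia's method (QTcF) is > 450 msec" as an exclusion.

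**The concern.** The two thresholds are joined by a bare conjunction, with no word such as both, either or each. Taken literally, the sentence describes a value that is above 450 msec and has also risen by more than 30 msec, which is one joint condition. It can equally be a short list of two things to mark. Two programmers could build different listings from it.

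The joint reading looks unattractive. The 30 msec limit would have no effect at baselines below 420 msec, because a subject there has to rise by more than 30 msec just to pass 450. This is the only QTcF marker in the SAP that is based on change, so a sizeable rise ending at or below 450 msec could go unmarked. Safety and tolerability are the secondary objective, so what is at stake is whether the safety listing draws attention to such rises.

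**Working it through.** The plan states no flag count or rate, so there is no figure of its own to reproduce.

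**1. What the joint reading would require.** A value must exceed 450 msec and exceed baseline by more than 30 msec, so the rise needed is more than max(30, 450 − baseline).

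| Baseline (msec) | Rise needed if joint (msec) |
|---|---|
| 370 | > 80 |
| 380 | > 70 |
| 390 | > 60 |
| 400 | > 50 |
| 410 | > 40 |
| 420 or above | > 30 |

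A change from 390 to 445 (+55) is unflagged. Above a baseline of 420, values from just over 450 up to baseline + 30 also miss the flag: up to 460 from 430, up to 470 from 440, up to 480 from 450. The general range flag may catch these, but its QTcF limits are not stated. Baselines at or below 450 are expected rather than guaranteed, because the exclusion sits under a clinical-significance qualifier and a screening heading. With separate flags, nothing is missed.

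**2. How many rows are involved.** Protocol Appendix 4, note e, schedules ECGs after the Day 1 dose on Day 2 (two), Day 6 (two), Day 12 (two) and Day 16 (one): 2 + 2 + 2 + 1 = 7. With up to 16 subjects, 7 × 16 = 112.

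**3. What share of rises above 30 msec a joint rule would leave unflagged.** The documents give no QTcF distribution, so these inputs are assumptions: normal subject means with between-subject SD 12 or 18, within-subject SD 8 or 10, mean shift 0, 10 or 20 msec, baseline at most 450. By simulation:

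| Assumed mean QTcF (msec) | Share of rises > 30 msec ending at or below 450 |
|---|---|
| 390 | 94–100% |
| 400 | 86–99.5% |
| 410 | 71–96% |
| 420 | 53–83% |
| 430 | 57–60% with no shift; 27–47% with a shift of 10–20 |

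The share is above half for assumed means up to 420 msec. At 430 msec with a positive shift it is below half.

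**4. How many such rises to expect.** The SD of a change is within-subject SD × √2.

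- No drug effect, within-subject SD 8: 8√2 = 11.3, z = 30/11.3 = 2.65, tail 0.0040, so 112 × 0.0040 = 0.45 rows.
- No drug effect, SD 12: 12√2 = 17.0, z = 1.77, tail 0.0385, so 112 × 0.0385 = 4.3 rows. All of these are measurement variability.
- Shift of 10 msec, SD 12: z = 20/17.0 = 1.18, giving about 13.4 rows. Here the shift would itself appear in the summarised mean changes, whichever flag rule is coded.

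**5. What each reading leaves visible.**

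| Item | Joint | Separate |
|---|---|---|
| Every ECG value and its change listed | yes | yes |
| Out-of-range values flagged, with significance call | yes | yes |
| Changes summarised by treatment and timepoint | yes | yes |
| Rise > 30 msec ending at or below 450 specifically marked | no | yes |
| Value > 450 with rise of 30 or less specifically marked | no | yes |

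SAP 8.1.1 indicates that continuous summaries carry the minimum and maximum, so the largest scheduled change at each timepoint should be visible in the table. That table leaves out post-dose repeat and unscheduled readings, but SAP 8.1 has all captured data listed.

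**The case for a change.** The strongest case for acting is that the sentence can be coded two ways and would take one line to settle. The general flag depends on the value reached and not on the change, so a rise from 390 to 445 msec might carry no mark at all if 445 lies inside the reference range. A 30 msec limit with no effect at baselines below 420 would be an odd thing to intend. The protocol also pays attention to QT: it reports a 15 msec mean QTc prolongation in male dogs (judged not adverse) and prohibits QT-prolonging drugs.

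The ambiguity stands, and so does the direction of its effect. Three parts of the case do not carry through. That most rises would be lost depends on an assumed QTcF distribution. That the listing is unspecified presumes the TFL shells are silent, which cannot be checked here. And neither reading is an error: a joint rule contradicts nothing in the protocol, so preferring separate flags is a matter of taste in how a listing is annotated.

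**Conclusion.** No change to the plan follows. This is loose wording about a listing marker, of the kind a programmer resolves from the TFL shells or with a question to the study statistician. Either answer gives a usable listing.

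The effect is confined to marks on at most 112 scheduled rows. No data are lost, the pharmacokinetic analysis is untouched, and SAP 8.6.6 plans no inferential safety analysis. No stopping rule or decision about a subject is tied to the flag. Clinical review does not depend on it either: adverse events noted on "ECG, vital sign measurements, or clinical laboratory evaluations" are recorded under protocol section 7.2.1, and Appendix 4, note u, has ECG results available to the investigator before release at end of treatment.

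The boundary arithmetic and the row count rest on the documents alone. The shares and expected counts rest on assumed QTcF distributions and show only a plausible range. The conclusion does not depend on them, because no result or conclusion of the trial changes under either reading.
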